**Effects of Flibanserin on the Pre- and Post-menopausal Female Brain**

**IRB16-0087**

**NCT02770768**

**Protocol Version 3/20/2019**

## **HSDD, EEG, and Flibanserin Study Detailed Protocol Narrative**

### **1. Background:**

Hypoactive sexual desire disorder (HSDD) is the most common sexual complaint in women. Over the past 8 years, [name] (née [name]) Ph.D. has developed and validated the Desire Intention task (DIT; e.g., Bolmont et al., 2014; Cacioppo et al., 2013; [name] & Bianchi-Demicheli, 2008), in which individuals are instructed to indicate as rapidly and as accurately as possible whether or not each visually presented stimulus (e.g., attractive persons of the opposite sex) is sexually desirable to them at the moment of the experiment. This task has been IRB approved previously (IRB#12-2229). In a functional magnetic resonance imaging (fMRI) study [name] discovered that women with HSDD, compared to normal controls, show a hypoactivation of the neural network known to sustain sexual desire in healthy non-HSDD individuals (Bianchi-Demicheli et al., 2011; Cacioppo & Hatfield, 2013; Cacioppo et al., 2012), including dopamine-rich limbic regions associated with reward processing, and a hyperactivation of brain regions involved when people view themselves from a third-person perspective (“spectatoring”) rather than from a first person perspective when viewing sexually desirable stimuli (Bianchi-Demicheli et al., 2011; Cacioppo and Cacioppo, 2013). A caveat with fMRI is that it does not inform us about the temporal dynamics between these brain areas. In 2008, [name] was also the first to identify the brain microstate underlying sexual desire in healthy non-HSDD subjects ([name] & Bianchi-Demicheli, 2008). The proposed study will be the first to address this question in patients with HSDD pre- and post-flibanserin.

Flibanserin (Addyi) is a new medication approved by the FDA for the treatment of pre-menopausal women with HSDD. We propose a study using the DIT to determine the extent to which flibanserin normalizes brain activity in women with HSDD and the extent to which regional brain activation is associated with changes in symptoms and behavior (as measures with self-report measures of sexual desire and eye-tracking movements).

## **2. Purpose:**

The research question of this double-blind randomized outpatient clinical trial is to determine the pre-post change in the Flibanserin group and investigate the extent to which Flibanserin normalizes brain activity in premenopausal and postmenopausal women with HSDD and the extent to which regional brain activation is associated with changes in symptoms and behavior (as measured with self-report measures of sexual desire and/or eye-tracking movements).

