Subjects will be recruited via Flyers posted on Campus and/or in Obstetrics and Gynecology practices and/or via ads posted on Craigslist by research coordinator, [name]. From these ads, interested individuals will be asked to go on Survey Monkey (<https://www.surveymonkey.com/r/HPENlabresearch>) and complete a survey that will help us determine whether they meet our selection criteria or email [name] at [[contact]](mailto:[contact]) or call the research team. Research coordinator will then contact individuals who may meet selection criteria. She and [name] and/or [name] will meet with them and give them the informed consent to read and go through it with the subjects. Upon receipt of a signed informed consent, participants will meet with [name] or [name] who will diagnose them with HSDD. If the subject does not have HSDD, she is not eligible to participate in the study. Subjects with a confirmed diagnosis of HSDD by [name] or [name] will then be randomly assigned by the UChicago Pharmacy/Investigational Drug Service to either Addyi (100 mg once daily at bedtime for 8 weeks, n = 60 subjects) or placebo (100 mg once daily at bedtime for 8 weeks, n = 60 subjects). The research question of this double-blind randomized outpatient clinical trial is to determine the pre-post change in the Flibanserin group and investigate the

extent to which Flibanserin normalizes brain activity in women with HSDD and the extent to which regional brain activation is associated with changes in symptoms and behavior (as measured with self-report measures of sexual desire and/or eye-tracking movements).

The study is registered on clinicaltrials.gov.

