## **6. Duration of Protocol:**

The total duration of the entire study on campus is 4.5 hours maximum. **Visit 1's duration:** 2 hours. Upon receipt of the subject's written consent, the subject will meet with [name] or [name] to have a diagnosis of HSDD confirmed, take a urine pregnancy test, and be asked to fill out questionnaires (duration 45 minutes maximum). Then, an IRB-approved member of the HPEN laboratory will walk the subject to the laboratory where the subject will be completing other questionnaires and performing the behavioral visual task while the subject's brain activity and eye movements are recorded (1h15 minutes maximum, including breaks and time to walk to the laboratory). At the end of Visit 1, a member of the HPEN laboratory will walk the subject to the pharmacy where they will receive either Flibanserin or Placebo. The HPEN member will not know what the patient receives (placebo or Flibanserin). One week after visit 1, a member of the study staff will contact the subject via telephone to see if the subject has experienced any side effects or if the subject has any questions. If any side effects are reported, the study staff will immediately contact [name] or [name] to confirm that any appropriate follow up is provided. **Phone call 2's duration:** 30 minutes. Two weeks after visit 1, the subject will be asked about any side effects she has experienced or is currently experiencing. The subject will also be asked to fill out some of the same questionnaires as visit 1 and answer questions about mood and sexual desire. **Visit 2's duration:** 1 hour. The subject will go directly to the HPEN laboratory, where the subject will perform the behavioral visual task again while the subject's brain activity and eye movements are recorded and fill out the same questionnaires the subject filled out during Visit 1. **Visit 3's duration:** 1 hour. The subject will again go directly to the HPEN laboratory to perform the behavioral visual task while the subject's brain activity and eye movements are recorded and fill out the same questionnaires as Visits 1 and 3.

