**Statistical Hypotheses:**

a. The research questions of this double-blind randomized study are: (a) to determine the pre-post change in the Flibanserin group vs. Placebo group in women with hypoactive sexual desire disorder (HSDD), (b) to compare the effect is Flibanserin (vs. placebo) on behavioral and brain changes between pre-menopausal women and postmenopausal women, (c) to investigate the extent to which post-Flibanserin's regional brain activations (compared to pre-Flibanserin's regional brain activations) are associated with changes in symptoms and behavior (as measured with self-report measures of sexual desire and/or eye-tracking movements), and (d) to investigate the extent to which Flibanserin normalizes brain activity in women with HSDD compared to matched healthy controls. The statistical hypotheses include the following:

i. Demographics: Statistical analyses for demographic and self-report measures will be computed using SPSS software. Prior to inferential analyses, descriptive statistics, including distributions, means, standard deviations, skewness, and kurtosis will be generated. Data will also be examined for the pattern and mechanism of missing data. Continuous data will be tested for normality and homogeneity of variance. Potential differences between the treatment and placebo groups in terms of demographic and behavioral measures will be explored using multivariate analysis of variance (MANOVA) or appropriate non-parametric tests as appropriate. Similar analyses will be performed to detect potential differences between the pre-menopausal subjects and the post-menopausal subjects. The overall significance level for these analyses will be at 5%, and effect sizes and confidence intervals will also be performed to test hypotheses about correlations.

ii. Behavioral data: Statistical analyses will be computed using SPSS software. Reaction times and performance data (ratings) will be screened. Prior to inferential analyses, descriptive statistics, including distributions, means, standard deviations, skewness, and kurtosis will be generated. Data will also be examined for the pattern

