atazanavir, ciprofloxacin, diltiazem, erythromycin, fluconazole, fosamprenavir, verapamil, paroxetine, carbamazepine, phenobarbital, phenytoin, rifabutin, rifampin, rifapentine, St. Johns Wort, digoxin, sirolimus, and some medicines used to treat high blood pressure, chest pain (angina), or other heart problems.

Drug interactions can be found in all tables including CYP3A4 inhibitors and CYP2C19 on:

<http://www.fda.gov/Drugs/DevelopmentApprovalProcess/DevelopmentResources/DrugInteractionsLabeling/ucm093664.htm>

Note: The use of moderate or strong CYP3A4 inhibitors is contraindicated in patients taking flibanserin, and flibanserin may interact with other medications (weak CYP3A4 inhibitors, strong CYP2C19 inhibitors, CYP3A4 inducers, and digoxin).

**Addyi is only available through the Addyi risk evaluation and mitigation strategy (REMS) Program because of the increased risk of severe low blood pressure and fainting (loss of consciousness) with alcohol use. By agreeing to participate in the present study and by signing the present consent form, the subject also agrees NOT to drink alcohol or beverages including alcohol while taking Addyi (Flibanserin), that is for a period of 8 weeks.**

If the subject feels that they won't be able to follow a non-alcoholic diet for 8 weeks, they will be asked to tell the research team. We will compensate them for their time spent with us.

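### Sections 2 and 5 word the research question as change within the flibanserin arm although the rest of the plan compares with placebo, and neither the primary EEG outcome nor question (c) has a named between-arm test

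*Combined protocol and SAP*

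**What the plan says.** Section 2 (Purpose) states: "The research question of this double-blind randomized outpatient clinical trial is to determine the pre-post change in the Flibanserin group". Section 5 (Methodology) repeats it: the question "is to determine the pre-post change in the Flibanserin group and investigate the" extent of normalisation of brain activity. Neither sentence names placebo.

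In Section 11, question (a) of the Statistical Hypotheses puts the same question differently: "to determine the pre-post change in the Flibanserin group vs. Placebo group". Question (c) asks how far "post-Flibanserin's regional brain activations (compared to pre-Flibanserin's regional brain activations) are associated with changes in symptoms and behavior", again with no placebo term.

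Other parts of the plan do use the placebo arm. Both aims in Section 3 are worded against placebo. The power statement in Section 10 is for a within-between interaction. The behavioural ANOVA in Section 11 has treatment as a factor, and a similar ANOVA is planned for eye-tracking. The effect-size criteria that close Section 11 refer to placebo for both the difference in desire (d > 0.48) and the associations (r > 0.48).

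The primary outcome is different. Section 4 defines it as EEG change from baseline at 8 weeks on either treatment. The Electrophysiological Data item in Section 11 describes the CENA toolbox but names no model and no treatment contrast. It then introduces meaningful change as each subject's change from before to after flibanserin.

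**The concern.** Change within one arm mixes any drug effect with everything else that happens over 8 weeks. The plan itself describes three such influences, all present in both arms:

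- The diagnosis is confirmed and the baseline recorded at Visit 1, and no run-in is described (Section 6).
- The subject "agrees NOT to drink alcohol or beverages including alcohol while taking Addyi (Flibanserin), that is for a period of 8 weeks" (Section 12), and the tablets are handed over at the end of Visit 1, after the baseline recording (Sections 6 and 25).
- At the later visits the subject will "perform the behavioral visual task again while the subject's brain activity and eye movements are recorded" (Section 6), so practice and habituation can change the responses.

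An analyst who follows Sections 2 and 5 and finds no contrast for EEG in Section 11 could report EEG change in the flibanserin arm as the trial's answer, even if placebo changed as much. Under question (c), a correlation present in both arms could be reported as the mechanism of the drug.

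**Working it through.** **1. The wordings side by side.**

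| Place | Comparator |
|---|---|
| Section 2; Section 5 | none (flibanserin arm only) |
| Section 3, Aims 1 and 2 | placebo |
| Section 10, Power | within-between interaction |
| Section 11, question (a) | placebo |
| Section 11, question (c) | none (flibanserin arm only) |
| Section 11, behavioural and eye-tracking ANOVA | treatment as a factor |
| Section 11, Electrophysiological Data | no model or contrast named |
| Section 11, association criteria | placebo mentioned; threshold r > 0.48; no test named |

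**2. The plan's own power figure.** Section 10 gives N = 120, alpha 0.05, effect size f = 0.14 and 95% power. It does not give the number of groups k, the number of measures m or the correlation rho. Taking k = 4 and m = 6 (2 stimuli x 3 visits) from the behavioural ANOVA, and assuming rho = 0.5 and sphericity:

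- lambda = N m f² / (1 - rho) = 120 x 6 x 0.0196 / 0.5 = 28.2
- df1 = (4 - 1)(6 - 1) = 15; df2 = (120 - 4)(6 - 1) = 580
- power = 0.948

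The figure reproduces under a between-group interaction. Other readings at rho = 0.5 give 0.927 (k = 2, m = 3), 0.860 (k = 2, m = 2) and 0.804 (k = 4, m = 3). The plan therefore sized the trial for a comparison between groups, though the statement does not say which interaction was meant.

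**3. Before-after test in the flibanserin arm.** Inputs: 60 per arm (Section 5), two-sided 0.05, zero drug effect, the same drift in both arms. The drift, in SDs of the change score, is assumed. The one-sample t test has noncentrality drift x √60. The between-arm test is a two-sample t test on change, simulated 20,000 times.

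| Drift | Noncentrality | Flibanserin only, significant | Between arms, significant |
|---|---|---|---|
| 0 | 0 | 5% | about 5% |
| 0.1 | 0.77 | 12% | not run |
| 0.2 | 1.55 | 33% | about 5% |
| 0.3 | 2.32 | 63% | about 5% |
| 0.4 | 3.10 | 86% | not run |
| 0.5 | 3.87 | 97% | about 5% |

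**4. Question (c).** A uniform drift shifts every woman equally and creates no correlation. To obtain one without a drug effect, the non-drug changes must vary between women and be correlated. Assume the same correlation r in both arms. The flibanserin-only test is t = r √(n - 2) / √(1 - r²) with n = 60. The between-arm test is the difference in Fisher z divided by √(2/57). Both were simulated 20,000 times.

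| Assumed r in both arms | Flibanserin only, significant | Between arms, significant |
|---|---|---|
| 0 | 5% | about 5% |
| 0.2 | 34% | about 5% |
| 0.3 | 66% | about 5% |
| 0.4 | 90% | about 5% |
| 0.48 | 98% | about 5% |

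**5. What the between-arm test of (c) can detect.** The standard error is √(2/57) = 0.187, with 60 per arm and no dropout.

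- r = 0.48 against 0: 0.523 / 0.187 = 2.79; power = Φ(2.79 - 1.96), about 80%.
- r = 0.48 against 0.3: (0.523 - 0.310) / 0.187 = 1.14; power = Φ(1.14 - 1.96), about 21%.

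**The case against.** The strongest reply is that the plan already compares with placebo almost everywhere, and that Sections 2 and 5 are loose summary sentences. Much of this stands. A reader of Section 2 alone might infer that a single-arm analysis is planned. The documents do not support that: no analysis section specifies a flibanserin-only test, and the aims, the power statement, question (a) and the ANOVA all point the other way. The reply does not cover the primary outcome, because the ANOVA with a treatment factor is written for reaction times, ratings and eye-tracking, not for EEG.

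A second reply is that the criteria closing Section 11 put the associations against placebo. They do, but they set only a threshold and name no test between arms. Read literally, the electrophysiological criterion relates change in flibanserin, not change in symptoms, to brain change. It is a basis for repairing (c) but does not repair it.

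Third, the size of any drift is unknown. That is right. A reader might infer that regression to the mean alone would produce a rise of about the plan's d = 0.48. The documents do not support this. Entry is by physician diagnosis with no scale cut-off, nobody is selected on EEG, and d = 0.48 is defined relative to placebo, so it is a different quantity from a within-arm rise. Practice and habituation need not move responses towards improvement. The timing of the alcohol stop is partly inferred: Section 12 ties it to taking the tablets, whereas Section 10 and the exclusion criteria speak of the duration of the study.

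**Conclusion.** The point holds as an inconsistency in the stated research question, with two consequences that need repair: no treatment contrast is named for the primary EEG outcome, and question (c) has no between-arm test. The randomised design is sound and can answer both questions.

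If the flibanserin-only wording were followed, a positive result could arise without a drug effect. The chance is 33% to 97% for an assumed drift of 0.2 to 0.5 SD of change at n = 60, against about 5% between arms. For (c) it is about 66% if non-drug changes correlate at an assumed 0.3. The drift sizes and correlations are assumptions, since the documents give none. The tempting stronger statement, that non-drug change would by itself answer both questions positively, goes too far: for the first question it depends on a drift of unknown size and direction, and for (c) uniform drift has no such effect.

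**What to change.** 1. In Sections 2 and 5, use the wording of question (a): the flibanserin versus placebo difference in change from Visit 1 to Visit 3. State that change within an arm is descriptive and supports no efficacy claim.
2. In the Electrophysiological Data item of Section 11, name the treatment-by-time contrast (Visit 1 to Visit 3) as the analysis of the primary EEG endpoint.
3. For question (c), in line with the placebo reference in the association criteria, estimate the association of brain change with symptom change in both arms. Report the placebo slope beside the flibanserin slope. Base any claim of a drug-specific mechanism on the arm x brain-change term with its confidence interval.

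The cost is wording and one interaction term, using data already collected in both arms. The downside is imprecision in step 3: power is about 80% for r = 0.48 against 0 but only about 21% for 0.48 against 0.3. The plan should therefore also say that a non-significant interaction is not evidence that the arms have the same association.

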## **3. Aims:**

Aim 1: By targeting deficits in subjective desire in postmenopausal women with hypoactive sexual desire disorder, flibanserin may offer a unique mechanism to address HSDD. Because of the pharmacology of flibanserin and its effects on the brain circuitry of emotion and its positive and already accepted effects on premenopausal women with HSDD, we hypothesize that subjective feelings and neurobehavioral responses to sexually desirable stimuli are improved after an 8-week intake of flibanserin versus placebo.

Aim 2: All women, independent of hormonal phase, should demonstrate similar responses. We hypothesize that similar changes should be observed in premenopausal and postmenopausal women after an 8-week intake of flibanserin versus placebo.

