## **10. Type and Number of Experimental Subjects:**

We expect to collect data from a total of 120 subjects between the age of 21 and 74 years. We will be testing premenopausal and postmenopausal women with hypoactive sexual desire disorder. Flibanserin is FDA approved for premenopausal but not postmenopausal women with HSDD. Women who are pregnant (or think they are pregnant), or who are nursing (or breastfeeding), or women who report not being able to stop drinking alcohol during the duration of the study will NOT be tested.

**Power:** Using G\* power calculation software (Version 3.1.9.2) for a within-between interaction in repeated measures ANOVA, a total sample size of 120 will yield 95% power to detect a significance, with alpha = .05 and an effect size of 0.14.

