and mechanism of missing data. A 2 (Treatment Type: Addyi or Placebo) x 2 (Group Type: pre- or post-menopausal) X 2 (type of stimuli: desired, nondesired) x 3 time (Visit 1, Visit 2, Visit 3) repeated-measures ANOVA will be performed on the reaction times and ratings to assess for main effects and interaction effects. P values, confidence interval, and effect sizes will be reported.

iii. Eye-tracking Data: A similar ANOVA will be performed for the following dependent variables: onset to first fixation and duration of fixation. As in our 2014's paper (Bolmont, Cacioppo, & Cacioppo), we will also analyzed include the subjects' visual area of interest (face vs. body) as a within-subject factors in our ANOVA.

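### Aim 2 predicts similar flibanserin effects before and after menopause, but the plan only tests for differences, names no contrast for the aim and gives no rule for concluding similarity

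*Combined protocol and SAP*

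**What the plan says.** Section 3 gives Aim 2 as a prediction of similarity: "We hypothesize that similar changes should be observed in premenopausal and postmenopausal women after an 8-week intake of flibanserin versus placebo". Section 11, Statistical Hypotheses, question (b), turns this into a neutral comparison of the drug effect ("vs. placebo) on behavioral and brain changes between pre-menopausal women and postmenopausal women").

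The model is in Section 11, item ii (behavioral data). Its factors are treatment and "Group Type: pre- or post-menopausal) X 2 (type of stimuli: desired, nondesired) x 3 time (Visit 1, Visit 2, Visit 3", and the "repeated-measures ANOVA will be performed on the reaction times and ratings to assess for main effects and interaction effects". It adds that "P values, confidence interval, and effect sizes will be reported". The eye-tracking item asks for a similar ANOVA and adds "visual area of interest (face vs. body) as a within-subject factors in our ANOVA". The electrophysiology item describes the EEG toolbox but gives no factors or contrast for the primary outcome. The self-report desire scales listed as secondary outcomes in Section 4 are not among the outcomes of item ii.

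The power statement in Section 10 is "for a within-between interaction in repeated measures ANOVA": 120 women "will yield 95% power to detect a significance, with alpha = .05 and an effect size of 0.14". It names no outcome and no factor.

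**The concern.** A hypothesis of similarity needs either an interval judged against a margin, or an estimate whose interval is reported without a claim of similarity. A difference test that comes out non-significant cannot tell similar effects from effects measured too imprecisely to distinguish.

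The plan also leaves open which result would count. The four-factor ANOVA has four terms containing treatment by menopausal group: alone, with stimulus, with time, and with both. Adding face versus body for eye-tracking makes eight. Terms without time average over all three visits, including the pre-treatment one. Terms with time have at least 2 degrees of freedom, so no term is by itself the 8-week difference that Aim 2 describes.

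Sections 5 and 10 note that flibanserin is not FDA approved for postmenopausal women. A conclusion that it works alike in both groups would therefore carry weight, and it should not rest on a test that is likely to be non-significant either way.

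**Working it through.** **The plan's own figure.** Take 0.14 as Cohen's f and use the standard noncentral-F calculation for a within-between interaction: λ = f²·N·m/(1 − r), with df (k − 1)(m − 1) and (N − k)(m − 1). Section 10 does not state the number of groups k, measurements m or correlation r. With k = 4, m = 6 (two stimuli × three visits) and r = 0.5:

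- λ = 0.0196 × 120 × 6 / 0.5 = 28.2, df 15 and 580, power 94.8%.

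So 95% can be reached, in this setting for a 15-df omnibus interaction. Other inputs also come close (k = 2, m = 4, r = 0.5 gives 96.5%). The figure concerns detecting an interaction and does not bear on similarity.

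**Inputs for the Aim 2 contrast.**
- 60 pre- and 60 postmenopausal women (Section 9) and 60 per arm (Section 5). Thirty per cell is an assumption, as no stratification is described.
- No dropout, equal variances, and pre-post correlation r from 0.3 to 0.8: assumptions.
- 0.48: borrowed from the drug-versus-placebo threshold (Cohen's d) in Section 11 to give a scale. The plan does not set it as a margin, and does not say which standard deviation it refers to, so both units are shown.

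**In standard deviations of change (change scores).** The contrast is (flibanserin − placebo, pre) − (flibanserin − placebo, post).
- SE = √(4/30) = 0.365
- 95% half-width = t(.975, 116) × 0.365 = 0.72; 90% half-width = 0.61
- Power for a true difference of 0.48 (noncentral t, 116 df) = 26%, so the test is non-significant 74% of the time

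**In baseline standard deviations.** Multiply the SE by √(2(1 − r)) for change scores, or by √(1 − r²) for a baseline-adjusted model (115 df).

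| r | Change score: 95% half-width | Power for 0.48 | Adjusted: 95% half-width | Power for 0.48 |
|---|---|---|---|---|
| 0.3 | 0.86 | 20% | 0.69 | 28% |
| 0.5 | 0.72 | 26% | 0.63 | 33% |
| 0.7 | 0.56 | 39% | 0.52 | 45% |
| 0.8 | 0.46 | 54% | 0.43 | 58% |

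A difference of 0.48 baseline standard deviations would thus be non-significant in about 42% to 80% of trials.

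**Chance of showing equivalence within ±0.48 when the true difference is zero.** This is the chance that the 90% interval lies inside the margin, approximately 2Φ(0.48/SE − 1.645) − 1, or zero if that is negative; checked by simulation.
- Margin in standard deviations of change: essentially 0% with change scores (the 90% half-width of 0.61 already exceeds 0.48), and under 3% with baseline adjustment.
- Margin in baseline standard deviations: 0% at r = 0.3, rising at r = 0.8 to 33% with change scores (SE 0.231) and 41% with adjustment (SE 0.219).

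**The case against.** Question (b) in Section 11 is worded neutrally, and the ANOVA's treatment-by-group terms do address it. The word similar in Aim 2 may be no more than an ordinary expectation in a mechanistic EEG study, for which a formal equivalence margin is not obligatory. The plan promises confidence intervals and effect sizes. A Visit 1 to Visit 3 contrast can be drawn from the ANOVA even though its time terms are omnibus, and Section 4 already fixes 8-week change as the quantity of interest.

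Much of this stands. A reader might infer that the sponsor will read p > .05 as similarity; the documents do not say so. A reader might also infer that the ANOVA cannot yield an 8-week difference; it can, but the plan does not name that contrast for Aim 2. Nor do the documents show the 95% power figure to be wrong: it is reachable under unstated inputs.

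What remains is that the aim is stated as similarity, the specified test is for difference, and nothing says how a result would be judged to support the aim.

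**Conclusion.** The point holds in this limited form and should be corrected. The stated test cannot support the stated hypothesis, no contrast is designated for Aim 2, and no rule for similarity appears in the text reviewed (Sections 7 and 19 were not available). Under the assumptions above, the 95% half-width is 0.72 standard deviations of change or 0.43 to 0.86 baseline standard deviations, and power for a difference of 0.48 is 26% or 20% to 58% respectively. These figures depend on 30 per cell and no dropout, and the baseline-unit ranges also on the assumed correlations; 0.48 is a yardstick only.

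It would go too far to say that the trial must be enlarged, or that an equivalence test is the only acceptable analysis. Estimation with an interval is a sound answer to Aim 2 at this sample size.

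The differing statements on who counts as postmenopausal (Sections 5 and 23, with the laboratory statement in Section 13) are a separate point. The sponsor must reconcile them, and nothing here depends on how.

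**What to change.** 1. Restate Aim 2 as estimating the difference in treatment effect between pre- and postmenopausal women.
2. Before unblinding, name one lead outcome at 8 weeks, defined as a single value per woman per visit. For an evoked potential or reaction time, say whether that is the desired-stimulus value or a difference between stimuli.
3. Model the week-8 value on treatment, menopausal group, their interaction and the Visit 1 value. The interaction coefficient is the Aim 2 estimate; report it with its 95% confidence interval. Report the same contrast for other outcomes as exploratory.
4. State that p > .05 will not be read as similarity, and that similarity may be claimed only if the 90% interval lies within a margin fixed before unblinding.
5. Keep the repeated-measures ANOVA as planned for the other questions.

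The cost is analysis-plan wording, a choice of lead outcome and, if a similarity claim is wanted, a margin, with IRB approval under Section 26. No new data are needed. The downside is a more modest Aim 2: with 120 women, similarity is likely to be inconclusive for any margin near 0.48.
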